6.5.2 Pharmacodynamic assessments

Corporate Confidential Information

Corporate Confidential Information

Soluble CD40 and soluble CD154

Peripheral blood total soluble CD40 and total soluble CD154 concentrations will be determined in Part 1, before, during and after administration of CFZ533. Only total soluble CD40 levels will be determined in Part 2.

6.5.2.1 Pharmacodynamic sample collection and processing

All blood samples will be taken by either direct venipuncture or an indwelling cannula inserted in a forearm vein. All samples will be given a unique sample number (as listed in [Appendix 1](#)). The details of sample processing, handling, storage, and shipment will be described in a separate laboratory manual.

6.5.2.2 Pharmacodynamic analytical methods

Analytical methods will be described in a separate laboratory manual.

6.5.2.3 Pharmacodynamic parameters

Corporate Confidential Information

Total soluble CD40 and total soluble CD154

Peripheral blood total soluble CD40 and total soluble CD154 (concentrations before, during or after treatment, as applicable) will be analyzed, as applicable.

6.6 Safety assessments

6.6.1 Physical examination

A complete physical examination should include the examination of general appearance, skin, neck (including thyroid), eyes, ears, nose, throat, lungs, heart, abdomen, back, lymph nodes, extremities, vascular and neurological systems. If indicated based on medical history and/or symptoms, rectal, external genitalia, breast, and/or pelvic exams may be performed.

Information for all physical examinations must be included in the source documentation at the study site and will not be recorded on the eCRF. Significant findings that are present prior to informed consent are included in the Relevant Medical History eCRF. Significant findings observed after informed consent signature which meet the definition of an AE must be appropriately recorded on the Adverse Event eCRF.

6.6.2 Vital signs

Vital signs (radial pulse rate, blood pressure and body temperature) will be recorded as indicated in the [Assessment schedule](#). Blood pressure and pulse rate will be assessed at the same arm each time of determination and after the subject has rested in the sitting position (may be supine if during hospitalization) for at least five minutes. Systolic and diastolic blood pressure will be measured three times using an automated validated device (e.g., OMRON) with an appropriately sized cuff. In case the cuff sizes available are not large enough for the subject's arm circumference, a sphygmomanometer with an appropriately sized cuff may be used.

The repeat sitting measurements will be made at up to 5 minute intervals and measurements will be recorded on the Vital Signs eCRF. Clinically notable vital signs are defined in [Appendix 7](#).

Body temperature should be measured as per local practice – the same method to be used consistently for all patients at each site.

6.6.3 Height and weight

Height in centimeters (cm) and body weight (to the nearest 0.1 kilogram [kg] in indoor clothing, but without shoes) will be measured.

Body mass index (BMI) will be calculated using the following formula:

- $BMI = \text{Body weight (kg)} / [\text{Height (m)}]^2$

Results will be recorded in the Vital Signs eCRF.

6.6.4 Laboratory evaluations

In the case where a laboratory assessment that is listed in the inclusion/exclusion criteria is outside of a **protocol-specified range** at screening and/or at the initial baseline, the assessment may be repeated once prior to randomization/enrollment. If the repeat value remains outside of protocol-specified ranges, the subject is excluded from the study.

Results from routine blood laboratory evaluation - directly assessed before Transplantation (i.e. within 24h prior to Tx) - can be used instead of further baseline laboratory evaluation. No second assessment implying second drawing of venous blood needs to be done.

In the case where a laboratory range is **not specified by the protocol**, but is outside the reference range for the laboratory at screening and/or initial baseline, a decision regarding whether the result is of clinical significance or not shall be made by the Investigator and shall be based, in part, upon the nature and degree of the observed abnormality. The assessment may be repeated once prior to randomization/enrollment.

In all cases, the Investigator must document in the source documents, the clinical considerations (i.e., result was/was not clinically significant and/or medically relevant) in allowing or disallowing the subject to continue in the study.

Clinically relevant deviations of laboratory test results occurring during or at completion of the study must be reported and discussed with Novartis personnel. The results should be evaluated for criteria defining an AE and reported as such if the criteria are met. Repeated evaluations are mandatory until normalization of the result(s) or until the change is no longer clinically relevant. In case of doubt, Novartis personnel should again be contacted.

Clinically notable laboratory findings are defined in [Appendix 7](#).

6.6.4.1 Hematology

Platelets, hemoglobin, red blood cell (RBC), white blood cell (WBC) and differential count (e.g., neutrophils, basophils, eosinophils, monocytes, lymphocytes) will be measured.

6.6.4.2 Clinical chemistry

Albumin, alkaline phosphatase, total bilirubin, bicarbonate/CO₂, calcium, cholesterol, chloride, creatinine, CK, gamma-GT, glucose, HbA1c, LDH, inorganic phosphorus, lipase, amylase, magnesium, potassium, total protein, AST, ALT, sodium, triglycerides, BUN and uric acid will be measured. At timepoints on 6h, 24h, 48h and 72h samples have to be taken only for Mg, K, creatinine, Ca and glucose.

If the total bilirubin concentration is increased above 1.5 times the upper limit of normal, direct and indirect reacting bilirubin should be differentiated.

6.6.4.3 Urinalysis

The following parameters will be measured: protein, creatinine, albumin, glucose; proteinuria and albuminuria per 24hr period will be estimated from spot protein/creatinine and albumin/creatinine ratios.

If the dipstick result is positive for protein, nitrite, leucocytes and/or blood the sample will be sent for microscopic analysis of WBC, RBC and casts according to local practice.

Local practice for transplant patients is that **no** microscopic analysis of the urine is done **for the first two weeks** after transplantation.

- Within the first two weeks after transplantation additional microscopic analysis will only need to be performed if the dipstick result is 3+ (or more) positive for leucocytes and/or blood (no WBC, RBC cast is expected to be seen with only proteinuria).
- From visit 108 (Study Day 29) onwards a microscopic analysis should be performed, except if the dipstick is completely negative.

6.6.4.4 Special clinical laboratory evaluations

The details of sample processing, handling, storage, shipment and analysis for the following assays will be described in a separate laboratory manual, as required.

6.6.4.5 Renal Function

Renal function will be assessed by calculated eGFR using the MDRD formula.

6.6.4.6 Coagulation studies

Coagulation studies will be performed, including prothrombin time (PT) and activated partial thromboplastin time (aPTT).

6.6.4.7 Cytokine assessment

Blood samples will be collected during the study (see [Assessment schedule](#)) for cytokine assessment via multiplex cytokine (or similar) platform (e.g., IL-2, IL-12, IFN-gamma, IL-4, IL-5, IL-10, IL-13, IL-1b, IL-6, IL-8, TNF-alpha, IL2R) and analyzed centrally, triggered by safety signals such as for example:

- hyper acute rejection or tBPAR associated with CFZ533 administration or in close proximity to the administration of CFZ533

- a febrile response around the time of CFZ533 administration as an indicator of an inflammation

6.6.4.8 Donor specific antibodies (DSA)

Blood samples for donor specific antibodies (antibodies directed against antigens expressed on donor organs) will be collected and evaluated locally.

6.6.4.9 Immunogenicity

The presence of anti-CFZ533 antibodies will be determined using a bridging ELISA-based assay.

Corporate Confidential Information

6.6.4.11 Viral tests and EBV/CMV/BK virus surveillance

All subjects will be screened/monitored for hepatitis B, hepatitis C, HIV, Epstein-Barr Virus (EBV), cytomegalovirus (CMV) and BK virus per local center practice. For centers where no protocol exists, details on the assessment requirements will be provided in the laboratory manual. Results of these assessments are to be transcribed into the appropriate eCRF pages.

6.6.5 Electrocardiogram (ECG)

The Fridericia QT correction formula (QTcF) will be used for clinical decisions.

Single 12 lead ECGs are collected. The original ECGs on non-heat-sensitive paper, appropriately signed, should be collected and archived at the study site.

Each ECG tracing should be labeled with study number, subject initials, subject number, date and time, be appropriately signed and dated to confirm review and filed in the study site source documents. For any ECGs with subject safety concerns, two additional ECGs should be performed to confirm the safety finding. Clinically significant ECG findings prior to dosing with investigational treatment must be discussed with the sponsor.

Clinically significant abnormalities should be recorded on the relevant section of the Medical History/Current Medical Conditions/AE eCRF page as appropriate.

6.6.6 Pregnancy

Pregnancy tests will be required for all females of child-bearing potential at timepoints as designated in the Assessment Schedule, and defined below.

Serum or urine pregnancy tests should be carried out according to local practice. Local result must be available and negative prior to randomization/enrollment.

6.6.7 Tuberculosis surveillance

Patients should have no history of active tuberculosis (per their pre-transplant assessments). A tuberculosis (TB) test (e.g. QuantiFeron, PPD or chest X-ray) will be conducted during screening whenever local procedures will allow (e.g. for living donors). For patients enrolled in areas where TB is endemic or who are at higher risk of active or latent TB disease, local screening result should be available and negative prior to randomization/enrollment for recipients of transplants from living donors. For deceased donor transplants a TB test showing negative results performed within 6 months prior to enrollment/ randomization is acceptable. Samples for a TB test will be collected at baseline and at various time points throughout the conduct of the study as defined in the [Assessment schedule](#). Chest X-ray to verify or monitor TB status of the patients is acceptable depending on local regulations. Whenever during the course of the study a positive test for TB is being confirmed, the patient will be discontinued from study treatment and returned to SoC.

6.7 Pharmacokinetic assessments

See Sample log tables ([Appendix 1](#)).

6.7.1 PK Blood collection and processing

All blood samples will be taken by either direct venipuncture or an indwelling cannula inserted in a forearm vein. Details of sample processing, handling, storage and shipment will be described in a separate laboratory manual. All samples will be given a unique sample number and a collection number (as listed in the blood log, [Appendix 1](#)). The actual sample collection date and time will be entered on the PK blood collection page of the eCRF. Sampling problems will be commented in the eCRFs.

6.7.2 Pharmacokinetic analytical methods

Analytical methods will be described in a separate laboratory manual.

6.7.3 Pharmacokinetic parameters

For standard PK abbreviations and definitions, see the list provided at the beginning of this protocol.

If data permit, typical exposure metrics and parameters could be determined using the actual recorded sampling times and non-compartmental method(s) with WinNonlin Pro or Phoenix, including (but not limited to): Cmax, Cmin, Ctrough, Tmax, , AUCt, from the plasma concentration-time data.

Concentrations below the LLQ will not be considered for PK parameter calculations.

Corporate Confidential Information

Defining bioavailability using the ratio of dose-normalized AUC approach, or the ratio of doses that provide equal AUCs approach, could be misleading (even if identical doses are administered IV and SC). Indeed, a non-compartmental approach, requires linear kinetics even if the same IV and SC doses are used. For mAbs, subject to target mediated disposition, clearance and distribution are dose/concentrations-dependent. A dose-independent, model-based analysis of IV and SC data would be the best way to determine bioavailability in this study. Such analysis may be reported in a separate standalone report.

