9.5.5 Pharmacokinetics

CFZ533 plasma concentration data will be listed by treatment, subject, and visit/sampling time point. Descriptive summary statistics will be provided by treatment and visit/sampling time point, including the frequency (n, %) of concentrations below the LLOQ, which will be reported as zero. Summary statistics will include mean (arithmetic and geometric), SD, CV (arithmetic and geometric), median, minimum and maximum. Concentrations below LLOQ will be treated as zero in summary statistics. A geometric mean will not be reported if the dataset includes zero values.

If data permit, PK parameters will be calculated as described in [Section 6.7.3](#) and will be listed by treatment and subject. Concentrations below the limit of quantification will not be considered for the calculation of PK parameters. Descriptive summary statistics will include mean (arithmetic and geometric), SD, and CV (arithmetic and geometric), median, minimum and maximum. An exception to this is Tmax where median, minimum and maximum will be presented.

A dose-independent, model-based analysis of IV and SC dosing may be used to determine the bioavailability of the SC administration in this study (see [Section 6.7.3](#) for more details). Also, any dose(concentration)-exposure relationship should be derived using same the approach. Such analysis will be reported in a separate standalone report.

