5.1 Variables

If data permit, typical exposure metrics and parameters could be determined using the actual recorded sampling times and non-compartmental method(s) with WinNonlin Pro or Phoenix, including (but not limited to): Cmax, Cmin, Cmin,ss, Tmax, from the plasma concentration-time data.

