5.2 Descriptive analyses

CFZ533 plasma concentration data will be listed by treatment, transplant status (if required), patient, and visit/sampling time point. Tac and MPA trough levels will be measured and listed by treatment, visit and patient. If data permit, PK parameters will be calculated and listed by treatment and patient. Concentrations below the limit of quantification will not be considered for the calculation of PK parameters. Descriptive summary statistics will include mean (arithmetic and geometric), SD, and CV (arithmetic and geometric), median, minimum and maximum. An exception to this is Tmax where median, minimum and maximum will be presented.

Corporate Confidential Information

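### The rule excluding values below LLOQ has no visible exception for Cmin, Ctrough and Cmin,ss, so the derived-parameter summary of trough exposure can only err upward

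*Protocol*

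**What the plan says.** The plan has two rules for CFZ533 concentrations below the limit of quantification.

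- **Derived PK parameters: BLQ is excluded.** Protocol 6.7.3 says "Concentrations below the LLQ will not be considered for PK parameter calculations". SAP 5.2 says "Concentrations below the limit of quantification will not be considered for the calculation of PK parameters", and protocol 9.5.5 has the same rule. The parameters covered are, in protocol 6.7.3, "including (but not limited to): Cmax, Cmin, Ctrough, Tmax" and an AUC, and in SAP 5.1, "Cmax, Cmin, Cmin,ss, Tmax". Ctrough is thus named only in the protocol list and Cmin,ss only in the SAP list. Cmin is in both.
- **Concentrations by treatment and visit: BLQ is kept.** Protocol 9.5.5 says "Concentrations below LLOQ will be treated as zero in summary statistics". It asks for descriptive statistics "including the frequency (n, %) of concentrations below the LLOQ, which will be reported as zero", and adds "A geometric mean will not be reported if the dataset includes zero values".

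The protocol's list of pharmacokinetic definitions describes Cmin,ss as the smallest concentration seen within a steady-state dosing interval. Footnote 11 to the assessment schedule requires samples on dosing days to be drawn before the dose.

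**The concern.** Leaving out BLQ values is ordinary practice when fitting a terminal slope or computing an AUC. It does not suit a minimum. A parameter defined as the lowest value cannot be derived correctly by a rule that throws away the lowest results.

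The statistics listed for the parameters in protocol 9.5.5 and SAP 5.2 (means, SD, CV, median, minimum, maximum) include no BLQ count. A reader of that table could not tell that a patient had been left out or given a higher value, and the printed minimum could not fall below LLOQ. At a visit with a BLQ result the concentration table also drops its geometric mean, so the only geometric mean trough left would be the parameter table's, which excludes that result.

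The low tail matters here. Exposure over the 12-month treatment period is a secondary objective of Part 2 (protocol 2.2.2), and the results are meant to guide dose and regimen selection (protocol 1.2). Protocol 5.5.5 itself links under-dosing to loss of immunosuppression.

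**Working it through.** The documents state no figure on this point: no LLOQ, no expected BLQ rate, no trough mean. There is nothing to reproduce. The check is a direction argument followed by an illustration.

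**Direction.** Take n patients, of whom k have a BLQ trough with true value b below LLOQ. Let M be the mean of the n − k quantifiable troughs, so M is at least LLOQ and exceeds b.

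- If the k parameters become missing, the table reports M. The mean over all n would be ((n − k)M + kb)/n, which is smaller than M whenever k is above 0.
- If each is replaced by another quantifiable value w from the same interval, the table reports ((n − k)M + kw)/n. This is again too high, by k(w − b)/n, because w is at least LLOQ and so exceeds b.

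Both routes go upward. Which one applies depends on the PK sampling times, which are redacted in the public copy.

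**Illustration for the missing case.** Inputs: n = 6 (Arm 1) and n = 30 (Arm 2A), from protocol 5.2. The counts k are assumed. If BLQ results are kept at v × M, then

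ratio = (mean with BLQ dropped)/(mean with BLQ kept) = n/((n − k) + kv).

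v = 0 is the protocol's own rule for concentrations. v = 0.1 and v = 0.5 are assumed alternatives, because zero is itself somewhat low for a value that is merely below LLOQ.

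| n | k (assumed) | v = 0 | v = 0.1 | v = 0.5 |
|---|---|---|---|---|
| 6 | 1 | 6/5 = 1.20 | 6/5.1 = 1.176 | 6/5.5 = 1.091 |
| 6 | 2 | 6/4 = 1.50 | 6/4.2 = 1.429 | 6/5 = 1.20 |
| 30 | 1 | 30/29 = 1.034 | 30/29.1 = 1.031 | 30/29.5 = 1.017 |
| 30 | 3 | 30/27 = 1.111 | 30/27.3 = 1.099 | 30/28.5 = 1.053 |
| 30 | 6 | 30/24 = 1.25 | 30/24.6 = 1.22 | 30/27 = 1.111 |

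With k = 0 every ratio is 1.

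**Disagreement between tables.** At v = 0 the ratio is also the factor by which the two planned outputs would differ if built from the same pre-dose samples. The concentration table divides by n with zeros included, and the parameter table divides by n − k.

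**The case against.** A reader might infer that a patient who loses exposure disappears from the trough reporting, so that the regimen looks adequate and any link between exposure and rejection is hidden. The documents do not support that.

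- Because dosing-day samples are pre-dose, the by-visit concentration table in protocol 9.5.5 is itself a trough summary. It keeps BLQ results as zero, counts them, and would print a minimum of zero.
- Concentrations are listed by patient (protocol 9.5.5, SAP 5.2) and plotted as individual profiles (SAP 5.2.1). The visible PK/PD plan in protocol 9.5.6 uses concentrations, not Cmin.
- Loss of effective exposure is not the same as a BLQ result. For a similar anti-CD40 antibody, protocol 1.1.2 puts loss of target saturation below 15 µg/mL. A value that low but above LLOQ would be kept under either rule.
- BLQ troughs may be rare. Protocol 3.3 reports more than 90% CD40 saturation on B cells for about four weeks after 3 mg/kg in healthy volunteers.

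The parameters are also conditional on the data permitting them, and redacted text follows the rule in both protocol 6.7.3 and SAP 5.2, so an exception there cannot be ruled out. For the same reason, the absence of the zero rule from the visible SAP text should not be counted as an omission.

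These points stand, and they confine the problem to the derived-parameter summary. They do not remove it. The visible rule has no exception for a minimum, and the BLQ count is promised for the concentrations but not for the parameters.

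**Conclusion.** The point holds for the derived-parameter summary only. Followed as written, the exclusion makes Cmin, Ctrough or Cmin,ss missing or too high whenever the trough is BLQ, and that summary can then disagree with the concentration table. The direction is certain. The size is not, since it depends on an LLOQ and a BLQ rate that the documents do not give. The +20% (1 of 6) and +11% (3 of 30) figures rest on assumed counts, on the BLQ result being the patient's only contribution to the parameter, and on zero as the benchmark. Keeping BLQ at an assumed 10% of the quantifiable mean lowers them to +17.6% and +9.9%. With no BLQ trough there is no effect.

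No visible success criterion uses these parameters, and the tBPAR analysis is unaffected. Severity: minor.

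**What to change.** In protocol 6.7.3 and 9.5.5 and in SAP 5.2, limit the BLQ exclusion to AUC and other curve-based calculations. For Cmin, Ctrough and Cmin,ss, keep a BLQ result as below LLOQ, in line with the concentration table. Report n and % BLQ beside the parameter, with a median and range in which BLQ ranks lowest. These statistics need no substituted value, apart from the case where half or more of the results are BLQ, when the median is simply shown as below LLOQ. The protocol text has to change as well as the SAP, because the SAP covers Part 2 only.

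The cost is a sentence or two in each document and minor programming. Reported troughs will be slightly lower when BLQ values occur.

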6.8 Other assessments

Corporate Confidential Information

7 Safety monitoring

7.1 Adverse events

An AE is any untoward medical occurrence (i.e., any unfavorable and unintended sign [including abnormal laboratory findings], symptom or disease) in a subject or clinical investigation subject. Therefore, an AE may or may not be temporally or causally associated with the use of a medicinal (investigational) product.

For all subjects who have signed informed consent and are entered into the study will have all adverse events occurring after informed consent is signed recorded on the Adverse Event eCRF.

Pre-existing medical conditions/diseases (i.e., Medical History(ies)) are considered AEs if they worsen after providing written informed consent. Abnormal laboratory values or test results constitute AEs only if they induce clinical signs or symptoms, or are considered clinically significant, or they require therapy.

The occurrence of AEs should be sought by non-directive questioning of the subject at each visit during the study. AEs also may be detected when they are volunteered by the subject during or between visits or through physical examination, laboratory test, or other assessments.

AEs must be recorded on the Adverse Event eCRF under the signs, symptoms or diagnosis associated with them, and accompanied by the following information:

1. the severity grade
 - mild: usually transient in nature and generally not interfering with normal activities
 - moderate: sufficiently discomforting to interfere with normal activities
 - severe: prevents normal activities
2. its relationship to the investigational treatment (no/yes), or other study treatment (non-investigational) (no/yes), or both or indistinguishable,
3. its duration (start and end dates) or if the event is ongoing, an outcome of not recovered/not resolved should be reported.
4. whether it constitutes a serious adverse event (SAE)
5. action taken regarding investigational/other study treatment
6. whether other medication or therapies have been taken (concomitant medication/non-drug therapy)
7. its outcome

An SAE is defined as any AE which meets any one of the following criteria:

- is fatal or life-threatening
- results in persistent or significant disability/incapacity
- constitutes a congenital anomaly/birth defect
- requires inpatient hospitalization or prolongation of existing hospitalization, unless hospitalization is for:
 - routine treatment or monitoring of the studied indication, not associated with any deterioration in condition
 - elective or pre-planned treatment for a pre-existing condition that is unrelated to the indication under study and has not worsened since signing the informed consent form
 - treatment on an emergency outpatient basis for an event not fulfilling any of the definitions of a SAE given above and not resulting in hospital admission
 - social reasons and respite care in the absence of any deterioration in the subject's general condition
- is medically significant, i.e., defined as an event that jeopardizes the patient or may require medical or surgical intervention to prevent one of the outcomes listed above.

All malignant neoplasms will be assessed as serious under "medically significant" if other seriousness criteria are not met.

Unlike routine safety assessments, SAEs are monitored continuously and have special reporting requirements; see [Section 7.2](#).

All AEs should be treated appropriately. Treatment may include one or more of the following: no action taken (i.e., further observation only); study drug dosage adjusted/temporarily interrupted; study drug permanently discontinued due to this AE; concomitant medication given; non-drug therapy given. The action taken to treat the AE should be recorded on the Adverse Event eCRF.

Once an AE is detected, it should be followed until its resolution or until it is judged to be permanent, and assessment should be made at each visit (or more frequently, if necessary) of any changes in severity, the suspected relationship to the study drug, the interventions required to treat it, and the outcome.

Information about common side effects already known about the investigational drug can be found in the Investigator Brochure (IB) or will be communicated between IB updates in the form of Investigator Notifications. This information will be included in the informed consent and should be discussed with the subject during the study as needed.

